4.2.2 Analysis of Secondary Variables

Quantitative variables (Vineland-3 Domains, FOS):

- Repeated measures ANOVA (procedure identical to primary variable).
- Bonferroni correction for multiple comparisons.
- Analysis of planned contrasts (linear and quadratic).

Ordinal variables (GAS):

- Friedman's test for repeated measures ($k = 3$ moments).
- Dunn's post-hoc comparisons with Bonferroni's correction.
- Analysis by individual objective (Objective 1, 2, and 3).

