9. STUDY PROCEDURES

9.1 Sampling Periods

Phase 1 - PRE-TEST (Baseline - Week 0):

- Control period during therapeutic admission.
- Vineland-3 administration, FOS to significant parents/caregivers.
- Elaboration of collaborative GAS objectives (parents-professionals).
- Complete interdisciplinary diagnostic evaluation.

Phase 2 - INTERVENTION (Weeks 1-14):

- Implementation of the Sentido's® Model according to the syllabus protocol.
- 4 weekly sessions of 60 minutes.
- Daily record of progress by professionals.
- Inclusion of caregivers (12 structured sessions), gradual fading of their participation in the sessions.

Phase 3 - POST-TEST (Week 15):

- Re-administration of Vineland-3, FOS, GAS evaluation after 14 weeks of intervention.
- Skills maintenance evaluation.

Phase 4 - FOLLOW-UP (Week 17):

- Third administration Vineland-3.
- Evaluation of GAS (parent-professional) objectives after two weeks without intervention.
- Post-intervention sustainability analysis.
- Return to usual intervention.

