2.2 Population Analysis

Target population: n = 24 estimated participants who meet inclusion criteria and complete evaluations in the three planned time points.

Pre-established criteria for inclusion in analysis:

- Participants aged 3-7 years with a confirmed diagnosis of ASD and/or associated DND according to DSM-V
- Signed informed consent
- Completion of the 14-week intervention protocol
- Complete data in the three temporary evaluations

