4.2 Inferential Analysis

4.2.1 Primary Variable Analysis

Main method: One-factor (time) repeated measures ANOVA with three levels.

- **Intrasubject factor:** Time (3 levels: week 0, 15, 17).
- **Dependent variable:** ABC Vineland-3 score.
- **Null hypothesis:** $H_0: \mu_0 = \mu_{15} = \mu_{17}$ (there are no differences between moments).
- **Alternative hypothesis:** H_1 : At least one mean differs.

Post-hoc comparisons: Bonferroni's method for multiple comparisons:

- Week 0 vs. Week 15.
- Week 0 vs. Week 17.
- Week 15 vs. Week 17.

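### The FOS is scheduled at weeks 0 and 15 only, but the SAP analyses it with an ANOVA that needs weeks 0, 15 and 17

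*Combined protocol and SAP*

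**What the plan says.** **Schedule (Protocol 9.1).** At week 0 the plan has "Vineland-3 administration, FOS to significant parents/caregivers". At week 15 it has "Re-administration of Vineland-3, FOS, GAS evaluation after 14 weeks of intervention". The week-17 list opens with "Third administration Vineland-3" and continues with "Evaluation of GAS (parent-professional) objectives after two weeks without intervention". The FOS is not on that list.

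**Analysis (SAP).** Section 4.2.2 has a block headed "Quantitative variables (Vineland-3 Domains, FOS"), whose first instruction is "Repeated measures ANOVA (procedure identical to primary variable"). SAP 4.2.1 defines the primary procedure with the within-subject factor "Time (3 levels: week 0, 15, 17") and post-hoc tests of all three pairs of visits. Section 4.2.2 adds linear and quadratic contrasts. SAP 4.5.2 fixes three comparisons per ANOVA, each at 0.0167. SAP 5.1 Step 4 repeats the ANOVA for the FOS.

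**Completeness and missing data (SAP).** Section 2.2 admits to the analysis those with "Complete data in the three temporary evaluations" and names no scale. Section 4.4.1 states a similar rule under the primary analysis. Section 4.4.2 lists LOCF as a sensitivity method.

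**The concern.** The SAP assigns the FOS a model that uses a measurement the visit schedule does not provide. The FOS is the plan's dedicated measure of family competence, confidence and care skills. These appear in the study hypothesis (Protocol 3), and the FOS is a listed secondary objective (Protocol 2.2, SAP 1.2).

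If the mismatch stays, the analyst has to improvise once the data are in hand: drop a time level, fill in a visit, or choose between 0.05 and 0.0167 for the one comparison that remains. SAP 8 does not list a change to a secondary analysis as either a minor or a major deviation, so nothing there clearly requires that choice to be recorded.

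**Working it through.** **1. Scales by visit, from Protocol 9.1**

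| Scale | Week 0 | Week 15 | Week 17 |
|---|---|---|---|
| Vineland-3 | given | given | given |
| GAS | goals set | evaluated | evaluated |
| FOS | given | given | not listed |

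No other section places the FOS at week 17. The general schedule (Protocol 4.4) and the procedural phases (6.1.1) mention administering and re-administering scales without visit weeks. The consent summary (10.2) refers to three phases and names the three scales, but does not say which scale is given in which phase.

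**2. The SAP's own figure.** With k = 3 visits there are k(k−1)/2 = 3 pairs, and 0.05/3 = 0.01667, which rounds to the stated 0.0167. The figure is correct for three visits and presumes three visits.

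**3. What the SAP procedure needs and what the schedule supplies.** Take n = 24 (SAP 2.2), with all 24 families completing the scheduled forms. Degrees of freedom for the time effect are (k−1) and (k−1)(n−1).

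| Quantity | k = 3 (SAP) | k = 2 (Protocol 9.1) |
|---|---|---|
| Degrees of freedom | 2 and 2 × 23 = 46 | 1 and 23 |
| Pairs | 3 | 1 |
| Alpha per pair | 0.0167 | 0.05 |
| Critical \|t\| on 23 df | 2.58 | 2.07 |
| Polynomial contrasts | linear, quadratic | linear only |
| Families with all k FOS scores | 0 of 24 | up to 24 of 24 |

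The F test on (2, 46), the quadratic contrast, and the pairs 0 vs 17 and 15 vs 17 cannot be estimated. The pair 0 vs 15 can. With two levels the ANOVA is the paired t-test (F = t²), which was confirmed numerically on simulated data, and sphericity does not arise. The SAP offers this pair only as a follow-up to the three-level F test. It also carries the 0.0167 threshold, which is stricter than a single comparison needs.

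**4. Whether LOCF would fill the gap.** Let d be the week 0 to 15 change. Copying week 15 into week 17 gives:

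- Time sum of squares = (2/3)·n·d̄², on 2 df.
- Error sum of squares = (2/3)·Σ(d − d̄)², on 2(n−1) df.
- F = n(n−1)·d̄² / Σ(d − d̄)² = t², the same value as the two-visit test.

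The week 15 to 17 difference is then exactly 0 with SD 0 for every family. The same F is read on (2, 46) instead of (1, 23) df, so the 5% critical value falls from 4.28 to 3.20. The probability that F(1, 23) exceeds 3.20 is 0.087, so an uncorrected test at a nominal 5% has a true level of about 8.7%. Epsilon is 0.5, so a Greenhouse-Geisser correction would restore (1, 23). However, SAP 4.3.1 makes that correction depend on Mauchly's test, and the contrast covariance matrix here is singular (determinant 0). LOCF adds no information about week 17.

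**The case against.** The strongest reply is that 9.1 may simply have left the FOS off the week-17 list. SAP 2.1 describes three time points without exempting any scale, and a planned quadratic contrast for the FOS suggests that its author expected three measurements. On the other side, the objectives state three time points for GAS (Protocol 2.2) and for the Vineland-3 domains (SAP 1.2), but not for the FOS. The documents do not settle the matter. This part of the reply stands: the omission cannot be called deliberate, and the remedy should not assume which section is wrong. One of the two must still change.

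A second reply is that the FOS is secondary. SAP 4.5.2 and 10.3 treat secondary outcomes as exploratory, and the main objective concerns adaptive behavior alone. That also stands and limits the weight of the point.

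Three stronger readings are tempting but not supported:

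- *The completeness rule excludes every child.* This needs SAP 2.2 to mean every scale at every visit, including a scale not scheduled there. The natural meaning is complete for what each visit schedules, and SAP 4.4.1 ties its rule to the primary analysis. The Vineland-3 is scheduled at all three visits.
- *The FOS has no usable data.* The week 0 to 15 change can be estimated for every family with both forms.
- *The plan will manufacture FOS maintenance through LOCF.* SAP 4.4.2 lists LOCF as a sensitivity method and does not mention the FOS or unscheduled visits. The maintenance outcome concerns skills (Protocol 7.2, SAP 1.2). The calculation above shows only what a misuse of the rule would do.

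**Conclusion.** The inconsistency is real. Taking Protocol 9.1 as written, the FOS analysis in SAP 4.2.2 and 5.1 Step 4 cannot be carried out as specified. The three-level F test, the quadratic contrast and two of three pairs are lost. The remaining pair, week 0 vs 15, has no stand-alone analysis and carries a threshold meant for three comparisons.

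The effect is confined to one secondary, exploratory outcome. The primary Vineland-3 analysis and its analysis set are unaffected, provided completeness is judged on what each visit schedules. The point should be corrected before the FOS is analysed, but it does not threaten the main result. The conclusion rests on 9.1 being the complete list of administrations. If the FOS is in fact given at week 17, the fault lies in 9.1 and the SAP analysis can stand.

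**What to change.** First establish at which visits the FOS is given, then make Protocol 9.1 and SAP 4.2.2 agree.

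- **If weeks 0 and 15 only:** in SAP 4.2.2 and 5.1 Step 4, take the FOS out of the three-level ANOVA. Specify the paired week 0 to 15 change with a 95% CI at alpha 0.05, as one comparison with no quadratic contrast and no sphericity test. State in 4.4.2 that LOCF is not applied to the unscheduled week-17 FOS.
- **If week 17 as well:** add the FOS to the week-17 list in 9.1 and keep the SAP analysis as it is.
- **In either case:** state in SAP 2.2 that completeness is judged per scale, at the visits where that scale is scheduled.

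The cost is a few lines of wording. Adding a week-17 FOS where none was planned would cost one 15-minute self-report (Protocol 8.3) at an existing visit, but is possible only for families who have not yet reached it. The documents do not say whether any remain; the Gantt chart ends recruitment in 2024 and runs follow-up to September 2025.

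### FOS is given a three-time-point analysis but is scheduled only at weeks 0 and 15; separately, the time metric for the polynomial contrasts on the Vineland-3 domains is not stated

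*Combined protocol and SAP*

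**What the plan says.** SAP 4.2.2 treats the Vineland-3 domains and FOS together. Each gets "Repeated measures ANOVA (procedure identical to primary variable"), Bonferroni-corrected comparisons, and "Analysis of planned contrasts (linear and quadratic"). The primary procedure in SAP 4.2.1 has the within-subject factor "Time (3 levels: week 0, 15, 17") and all three pairwise comparisons. Neither section gives contrast coefficients or a time metric.

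Protocol 9.1 sets out what is administered when:

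- Week 0: "Vineland-3 administration, FOS to significant parents/caregivers".
- Week 15: "Re-administration of Vineland-3, FOS, GAS evaluation after 14 weeks of intervention".
- Week 17: "Third administration Vineland-3" and "Evaluation of GAS (parent-professional) objectives after two weeks without intervention". FOS is not listed.

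SAP 2.2 admits to the analysis only participants with "Complete data in the three temporary evaluations", and makes no exception for FOS. SAP 4.4.1 repeats that restriction, and SAP 4.4.2 adds last observation carried forward (LOCF) as a sensitivity analysis.

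**The concern.** There are two separate problems.

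**FOS.** It is a named secondary outcome in both the protocol and the SAP, yet its planned analysis needs a third measurement that the visit schedule does not provide. The analyst would have to improvise after seeing the data. Under LOCF, every family's week-17 value would be a copy of its week-15 value.

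**Vineland-3 domains.** A linear or quadratic contrast has no definite meaning until the spacing of the time points is fixed. The gaps here are 15 weeks and 2 weeks. If coefficients for equal gaps were applied, a child improving at a constant rate would appear to level off after week 15, and a significant quadratic might be reported as slowing once the intervention stops.

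**Working it through.** The plan gives no figure for these contrasts, so there is none to reproduce.

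**1. FOS: what can be estimated**

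| Planned for FOS (SAP 4.2.1, 4.2.2) | Needs week 17? | Possible with weeks 0 and 15? |
|---|---|---|
| Three-level time effect | Yes | No; 1 df for time, not 2 |
| Quadratic contrast | Yes | No; design has rank 2 for 3 coefficients |
| Week 0 vs 15 | No | Yes |
| Week 0 vs 17 | Yes | No |
| Week 15 vs 17 | Yes | No |

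Applied to FOS, the completeness rule retains nobody, because no family has a third scheduled FOS. LOCF to week 17 would make the week 17 minus week 15 difference exactly 0 for every family: a plateau by construction.

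**2. Vineland-3 domains: effect of the metric**

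Under steady growth of b points per week, the means at weeks 0, 15 and 17 are 0, 15b and 17b.

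- Equal-spacing quadratic (1, -2, 1): 0 - 30b + 17b = -13b, although the true curvature is 0.
- Actual-spacing quadratic, proportional to (2, -17, 15): 0 - 255b + 255b = 0.

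For the same total gain G = 17b, a true plateau (0, G, G) gives -G on the equal-spacing contrast, and steady growth gives -(13/17)G = -0.765G. The ratio is about 76%, with the same sign.

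**3. How often the false quadratic would be significant**

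Inputs:

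- n = 24 (SAP 2.2).
- SD 15, the normative value (SAP 3.2.1); the SD in this sample is not given.
- Two-sided 0.05; SAP 4.5.1 states this for the primary analysis, and its use here is an assumption.
- Within-child correlation 0.64 to 0.92, an assumption borrowed from the test-retest range in protocol 8.1.
- Compound symmetry (assumed).
- Growth of 6 points per 15 weeks continuing at the same rate to week 17 (illustrative): means 0, 6.0, 6.8.

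Contrast: 0 - 2(6.0) + 6.8 = -5.2. A fully held gain (0, 6, 6) gives -6.0.

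SE = 15 × √[6(1 - ρ)/24] = 7.5 × √(1 - ρ). The probability comes from the noncentral t on 23 df.

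| ρ | SE | 5.2/SE | P(significant), equal spacing |
|---|---|---|---|
| 0.64 | 4.50 | 1.16 | 20% |
| 0.80 | 3.35 | 1.55 | 32% |
| 0.92 | 2.12 | 2.45 | 65% |

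For a total gain of 7.5 points, the bottom of the moderate band that SAP 5.2.1 defines for the composite, the range is 23% to 74%. Simulation of that 7.5-point case at ρ = 0.64 and 0.92 gave 24% and 73% with equal spacing, and about 5% with actual spacing.

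**4. What correct spacing does not achieve**

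Under the same assumptions, with results in the order ρ = 0.64, 0.80, 0.92:

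- The correctly spaced quadratic detects a true plateau (0, 6, 6) in about 6%, 7% and 9% of trials.
- The direct week 17 minus week 15 difference detects a continued gain of 0.8 points in about 6%, 7% and 10%.

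**The case against.** **The plan does not say equal spacing will be used.** A reader might infer from the three-level factor that the actual spacing will be ignored. The documents do not support that. SAP 4.2.1 labels the levels by week, SAP 6.3 promises a preset syntax file that is not shown, and no coefficients appear anywhere. What can be said is that the metric is unspecified. Every percentage for equal spacing in the working depends on that choice. This objection stands.

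**The harm is contained.** A reader might also infer that the maintenance conclusion rests on the quadratic. It does not: protocol 7.2 and SAP 1.2 define maintenance as week 15 against week 17, and that comparison is already planned. SAP 5.1 Step 4 does not mention the polynomials, SAP 5.2 gives no rule for interpreting them, the primary analysis has none, and SAP 4.5.2 and 10.3 treat secondary results as exploratory. This stands for the Vineland-3 domains. It does not help FOS, for which the week 15 vs 17 comparison is unavailable as scheduled.

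**A third FOS may simply have been left off the list.** Protocol 10.2 speaks of three phases of scales and names FOS among them, and protocol 4.4.1 includes FOS re-administration. But neither assigns FOS to week 17, and SAP 3.2.3 gives it no measurement times. The omission may be an oversight in the schedule, so the passages should be reconciled without presuming which one is wrong.

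**The completeness rule could be read across all instruments**, which would empty the primary analysis too. SAP 2.2 does not say the rule works that way, and only its effect on FOS is claimed here.

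**Conclusion.** The FOS conflict is firm and needs no numerical assumption. On the schedule in protocol 9.1, the only estimable FOS change is week 0 to week 15; the rest of the analysis in SAP 4.2.2 cannot be run.

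The Vineland-3 point is conditional and smaller. The missing metric is a gap in specification. If equal spacing were chosen, constant growth would be falsely flagged as curved in about 20% to 65% of trials for growth of 6 points per 15 weeks, under the assumed SD, correlations and compound symmetry, and with growth continuing unchanged after the intervention stops. It affects exploratory results only. Correct spacing restores the 5% error rate but leaves power of about 6% to 10% to tell continued gain from a held gain in the example. That limit comes from the 2-week gap and the sample size, not from the coding.

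**What to change.** 1. **Reconcile protocol 9.1 with SAP 2.2, 4.2.2 and 4.4** on whether FOS is measured at week 17. If the schedule stands as written, specify for FOS the paired week 15 minus week 0 change with a 95% CI. Remove FOS from the three-level ANOVA and the contrasts, and exempt it from the three-time-point completeness rule and from LOCF to week 17.
2. **For the Vineland-3 domains**, either state in the SAP and the syntax file that the polynomial metric is 0, 15, 17, or delete the polynomial contrasts and rely on the week 0 vs 15 and week 15 vs 17 comparisons already planned, each reported with its CI.
3. **Add a sentence to SAP 10** saying that the 2-week gap gives little power to distinguish continued gain from maintenance, so that a non-significant week 15 vs 17 result is not taken as proof of maintenance.

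The cost is SAP wording and one line of syntax. No new data are needed on the schedule as written; if a week-17 FOS was intended, the cost is one further caregiver questionnaire, put at 15 minutes in protocol 8.3, for any family whose week-17 visit is still to come.

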7.2 Secondary Variables

- Scores by Vineland-3 domains (Communication, Daily Life, Socialization).
- GAS scores for individualized goals.
- FOS scores for family competencies.
- Skill maintenance (week 15 vs. week 17).

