8.2 Goal Attainment Scaling (GAS)

Description: A method of personalized scales that allow quantifying progress towards specific collaboratively defined objectives.

Modified measuring system: 5-point scale adapted for EA and DND:

- -2 = current performance levels (baseline).
- -1 = progress.
- 0 = expected level of results.
- +1 = somewhat more than expected.
- +2 = much more than expected.

Conversion: Kiresuk-Sherman formula for standardized T-scores (M=50, SD=10).

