4.5 Significance Criteria and Adjustments for Multiple Comparisons

4.5.1 Level of Significance:

- **Primary analysis:** $\alpha = 0.05$ (bilateral).
- **Confidence intervals:** 95%.

4.5.2 Adjustments for Multiple Comparisons:

- **Within each variable:** Bonferroni correction for post-hoc comparisons.
- **Among secondary variables:** No adjustment (exploratory analysis).
- **Number of comparisons by ANOVA:** 3 post-hoc comparisons.

Bonferroni adjustment formula: $\alpha_{\text{ajustado}} = \alpha / \text{number of comparisons} = 0.05 / 3 = 0.0167$.

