5. SPECIFIC ANALYSIS PROCEDURES

5.1 Planned Sequence of Analysis

Step 1: Planned descriptive analysis of baseline characteristics and systematic evaluation of missing data.

Step 2: Protocolized verification of statistical assumptions for each variable according to prespecified methods.

Step 3: Planned analysis of primary variable (ABC Vineland-3):

- Repeated measures ANOVA according to protocol specifications.
- Post-hoc comparisons conditioned to significant F.
- Preset calculation of effect sizes.

Step 4: Scheduled analysis of quantitative secondary variables (Vineland-3 domains, FOS):

- Repeated measures ANOVA for each variable according to protocol.
- Post-hoc comparisons with prespecified Bonferroni correction.

Step 5: Planned ordinal secondary variable (GAS) analysis:

- Friedman's test for each objective according to design.
- Dunn's post-hoc comparisons according to protocol.

Step 6: Preset sensitivity analysis for missing data based on specified methods.

Step 7: Planned synthesis of findings and interpretation according to pre-established criteria.

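### For each GAS objective, Dunn's comparison after Friedman is badly underpowered for week 15 vs week 17, because week 0 sits at the scale floor

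*Combined protocol and SAP*

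**What the plan says.** SAP 4.2.2 treats GAS as ordinal and analyses Objectives 1, 2 and 3 separately over three moments, with Friedman's test followed by "Dunn's post-hoc comparisons with Bonferroni's correction". SAP 5.1, Step 5, repeats this: "Friedman's test for each objective according to design", then "Dunn's post-hoc comparisons according to protocol". Neither section says which ranks or which standard error Dunn's comparison uses.

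The scale in Protocol 8.2 defines its lowest level, after the minus sign, as "2 = current performance levels (baseline". Week 0 is therefore -2 for every child.

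Protocol 7.2 lists "Skill maintenance (week 15 vs. week 17" among the secondary variables, and SAP 1.2 makes it a secondary objective. SAP 2.2 expects "n = 24 estimated participants who meet inclusion criteria and complete evaluations in the three planned time points". SAP 4.5 sets a two-sided 0.05 level and a Bonferroni level of 0.0167 for three comparisons. The documents give no power figure, expected loss rate or equivalence margin for the GAS week 15 vs 17 contrast.

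**The concern.** Dunn's comparison after Friedman ranks the three moments within each child and judges the difference of two rank sums against a variance that holds when all three moments are exchangeable. Here one moment is fixed at the floor by definition. If a child is above baseline at both later visits, week 0 takes rank 1, and weeks 15 and 17 can only share or swap ranks 2 and 3. The rank difference between them is then -1, 0 or +1, yet it is judged against a yardstick built for differences of up to 2.

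Week 15 vs week 17 is where loss of skill after the intervention stops would show. If many children slip a level and the test stays non-significant, a reader could take the result as a sign that skills held. The comparison is naturally paired, and a paired test of the two visits does not need the baseline ranks.

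**Working it through.** **Inputs.** n = 24 complete cases (SAP 2.2); k = 3 moments, each objective tested separately (SAP 4.2.2 and Step 5); two-sided alpha 0.05 with three comparisons (SAP 4.5); week 0 = -2 (Protocol 8.2). The documents give no loss or gain rates, so those below are assumptions.

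**The plan's own figure.** 0.05 / 3 = 0.0167, as stated. The two-sided critical value is z = 2.394.

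**Dunn's yardstick.** The SD of a rank-sum difference is sqrt(n k (k+1) / 6) = sqrt(24 × 3 × 4 / 6) = sqrt(48) = 6.93. The critical rank-sum difference is 2.394 × 6.93 = 16.6.

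**What a child can contribute to week 15 minus week 17.** An unchanged child gives 0. A child who drops but stays above -2 gives 3 - 2 = 1. A child who drops to -2 ties with week 0 and gives 3 - 1.5 = 1.5. If no child returns to baseline, the variance of the sum when weeks 15 and 17 do not differ is at most 24 × 1 = 24, and less with ties, against the 48 that Dunn uses. A return to -2 contributes 1.5² = 2.25, so the bound of 24 does not cover that case.

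**Smallest number of losers that reaches significance, no child gaining (Bonferroni-adjusted p).**
- Dunn, losers stay above baseline: 16 gives z = 16 / 6.93 = 2.31, p = 0.063; 17 gives z = 2.45, p = 0.042. It needs 17 of 24.
- Dunn, all losers return to -2: 11 gives z = 16.5 / 6.93 = 2.38, p = 0.052; 12 gives z = 2.60, p = 0.028. It needs 12 of 24.
- Dunn, half of the losers return to -2: it needs 14 of 24.
- Exact sign test: 6 losers give unadjusted p = 2 × 0.5^6 = 0.031, above 0.0167; 7 give 2 × 0.5^7 = 0.0156. It needs 7 of 24.

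**Other forms of Dunn, losers staying above baseline.** With a tie-corrected SE, 15 of 24 losers is still non-significant (p = 0.069). With Dunn on the pooled ranks of all 72 scores, in an example where every child is at 0 at week 15 and losers drop to -1, 13 of 24 is still non-significant (p = 0.057).

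**Simulated power.** Assumed week-15 levels are 25/40/25/10% at -1/0/+1/+2, losers drop one level, and 2% gain. Repeat runs agree to about one percentage point.

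| Children losing a level | Dunn, usual SE | Dunn, tie-corrected SE | Exact sign test |
|---|---|---|---|
| 40% | 1% | 5% | 74% |
| 50% | 10% | 22% | 90% |
| 60% | 38% | 56% | 98% |

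At 70% loss, Dunn with the usual SE reaches about 74%.

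**Type I error.** With equal true chances of gain and loss and all children above baseline, Dunn's simulated error rate is at most about 0.0003 against the nominal 0.0167.

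**The case against.** Several points on the other side stand.

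- **Power is not absent everywhere.** A reader might infer that the test has almost no power at all, or that most children could always regress unnoticed. Power is about 38% at 60% loss and 74% at 70%. If every loser returns to -2, the largest missed loss is 11 of 24 (46%), which is not a majority.
- **The form of Dunn is not specified.** The rank-sum form with the untied SE is the usual one after Friedman, but it is an assumption. The alternatives narrow the gap without closing it.
- **The omnibus is not contradicted.** A reader might see a conflict between a significant Friedman test and a non-significant week 15 vs 17 contrast. There is none: if children improve from -2, week 0 drives the omnibus result.
- **The plan does not equate non-significance with maintenance.** No section states that rule, and a reader would have to supply it. Maintenance is also examined on the Vineland-3 composite and domains (SAP 4.2.1 and 4.2.2). SAP 4.1.2 plans GAS frequencies by category with CIs and bar charts by time, so a large net shift would be visible. Those are marginal counts, however, and do not show how many individual children lost, held or gained a level.
- **GAS is exploratory.** SAP 4.5.2 and 10.3 say so for secondary outcomes.
- **The baseline coding is not wholly consistent.** Protocol 8.2 puts baseline at -2, while SAP 5.2.2 labels -1 as no change and -2 as a setback. The calculation follows Protocol 8.2, and the two sections must be reconciled.
- **A paired test alone does not establish maintenance.** The sign test still misses 6 losers of 24. With one child gaining it needs 10 losers, and with two gaining it needs 12.

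**Conclusion.** The point holds as a loss of efficiency in a secondary, exploratory analysis that bears on a stated objective. For losses affecting about 40% to 60% of children, the planned comparison has far less power than a paired exact test at the same alpha, and no plausible form of Dunn recovers the difference.

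The 17, 12 and 7 of 24 thresholds rest on week 0 being -2, on 24 complete cases, on no child gaining and, for the first two, on the usual rank-sum SE and on where the losers land. They need no assumed loss rate. The power figures also depend on the assumed week-15 distribution and the 2% gain rate. The primary Vineland-3 analysis is not affected.

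**What to change.** In SAP 4.2.2 and 5.1, Step 5, replace Dunn's comparisons with paired exact tests (sign or Wilcoxon signed-rank, with one named in advance) for all three pairwise comparisons per objective, at the same Bonferroni level of 0.0167. Covering all three pairs avoids leaving the two baseline contrasts without a method.

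For week 15 vs week 17, add a table per objective with the numbers of children better, same and worse and their 95% CIs. State that a non-significant result alone does not show maintenance. The counts and intervals matter as much as the change of test, because only they show how much loss the data leave open.

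The cost is SAP wording and a few lines of syntax. No new data are needed.
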